1.2 Hypotheses

1.2.1: Compared to TAU: MBCT-S subjects will experience a longer duration from baseline until a suicide event.

1.2.2: Compared to TAU: MBCT-S subjects will experience a greater decrease in suicide events during the study period.

1.2.3: Compared to TAU, MBCT-S subjects will experience a longer duration from baseline until a suicide attempt.

1.2.4: Compared to TAU: MBCT-S subjects will have lower scores on the Beck Scale for Suicide Ideation, the Beck Depression Inventory and the Beck Hopelessness Scale.

2. Background and Significance

Strategies for reducing the risk of suicide are a top priority within the VA. Every month the VA becomes aware of approximately 1,100 veterans in VA care who attempt suicide. Although VA suicide prevention efforts seem to improve safety for some groups of veterans, VA data show that 11% of veterans with one suicide attempt make a re-attempt within 9 months.

There is a significant gap in the availability of evidence-based psychotherapies targeting suicide. While the VA has implemented most components of the multifaceted prevention approach recommended in a 2009 VA report on suicide,¹ it has yet to implement nationally any evidence-based psychotherapies targeting suicide. This gap may be due, in part, to the dearth of evidence-based therapies addressing suicide. The 2009 VA report, which identified only one small randomized controlled trial (RCT) with veterans and a handful with non-veterans, cited the pressing need for high-quality RCTs testing specialized therapies for those at suicide risk, a recommendation reiterated in a 2011 report commissioned by the Suicide Prevention Resource Center (SPRC),² which cited a "desperate" need for suicide-focused therapies.

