4.2 Dependent Variables or Outcome Measures

Our primary outcome/dependent variable is suicide "events," including both attempts and serious ideation. While we will also examine suicide attempts as a secondary outcome, we are limiting our primary outcome to events because of the anticipated low incidence of attempts during our 12-month follow-up period.

We are defining both events and attempts according to the VA's standardized Self-Directed Violence Classification System (SDVCS). An "event" will be defined as the occurrence of one or more of the following: (a) suicidal ideation with suicidal intent, with or without a specific plan; (b) preparatory behaviors; (c) deliberate self-directed violence, with or without injury, including actual attempts or attempts that are interrupted or aborted, in which evidence of intent is either indeterminate or clear. Suicide attempts, defined according to the SDVCS, will include deliberate self-directed violence that: (a) is actual or interrupted by self or others: (b) results in injury or the potential for injury; (c) includes evidence of suicidal intent which is explicit, implicit or unclear. We will operationalize the above definition of suicide events and attempts using the Columbia Suicide Severity Rating Scale (C-SSRS).

In addition to measuring differences between treatment groups with respect to the above outcomes, we will also explore the effect of treatment group on measures of suicide ideation, depression and hopelessness. Suicide ideation will be measured utilizing two instruments – the Beck Scale for Suicide Ideation, which is the gold standard for ideation measurement and provides a dichotomous (yes-no) measure of the presence or absence of ideation, and the C-SSRS, which provides a measure of ideation severity. Depression will be measured utilizing the Beck Depression inventory and hopelessness, the Beck Hopelessness Scale. In addition, we will use the MINI International Neuropsychiatric Interview (MINI)⁵ to obtain a standardized psychiatric diagnosis and subscales from the Brief Psychiatric Rating Scale to screen patients for eligibility at study enrollment. We will also administer the Experiences Questionnaire to assess the acquisition of mindfulness skills as a result of the intervention. The instruments and data sources we will utilize to measure these outcomes, along with the timeframes for instrument administration/data collection, are described below.

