Columbia Suicide Severity Rating Scale ⁶(C-SSRS) will be used at baseline and at each follow-up point to measure the occurrence of our two primary outcomes: a *suicidal event* and a *suicide attempt*. Designed to quantify the severity of suicidal ideation and behavior, the scale provides information on the presence or absence of active suicidal thoughts, method and/or intent and severity of ideation, determined according to such factors as frequency, duration, controllability, deterrents and reasons. The scale also assesses self-injurious behavior, whether the behavior was interrupted or aborted, preparatory acts and the actual and potential lethality of the behavior. In three multisite studies with adolescents and adults, the C-SSRS demonstrated good convergent and divergent validity with other multi-informant suicidal ideation and behavior scales and had high sensitivity and specificity for suicidal behavior classifications compared with another behavior scale and an independent suicide evaluation board.

*Beck Scale for Suicide Ideation*⁷ (SSI) In addition to the C-SSRS, we will use the SSI as a separate measure of *ideation severity*. The 21-item clinician-administered SSI, administered at baseline and at all follow-ups, is one of the most widely-used measures for detecting and measuring the intensity of the patients' attitudes, behaviors, and plans to commit suicide during the past week. The SSI has been standardized

with adult inpatient and outpatient psychiatric patients, including men and women of diverse racial/ethnic backgrounds and ages. It has demonstrated moderately high internal consistency, with Cronbach coefficient alphas ranging from .84 and high inter-rater reliability, with correlations ranging from .83 to .98. The SSI is significantly associated with suicide items from the Beck Depression Inventory and the Hamilton Rating Scale for Depression as well as with previous suicide attempts and depression severity, discriminating suicidal inpatients from depressed outpatients and suicide attempters from non-attempters.

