For H_{2a} analysis will be similar to that described in H1a. Specifically, Cox proportional-hazards regression model analyses will be run at 12 months post-baseline to analyze and compare across groups the survival-time to the first suicide attempt.

For H_{3a} we will measure suicidal ideation using two scales – the Beck Scale for Suicide Ideation (SSI) and the Columbia Suicide Severity Rating Scale (C-SSRS). The SSI is the gold standard for measuring suicide ideation and will provide data that has comparability to other studies. The SSI, however, only allows calculations of suicide severity for those screening positive for ideation and so produces scores that tend to be highly skewed. For that reason, we are using the SSI to determine presence or absence of ideation, but will also use the C-SSRS to measure severity of ideation since it allows all subjects to be included in the analysis. The C-SSRS severity scale ranges from 0 "no ideation present" to 5 "active ideation with plan and intent." Similarly, intensity of ideation will be measured using the C-SSRS intensity scale, which ranges from 0 "no ideation" to 25 "most intense."

The analysis for H3a will examine 3 aspects of suicide ideation - presence of active ideation, ideation severity and ideation intensity. Our first analysis will treat ideation as a dichotomous variable (present or absent), with a response of "0" on both SSI screening items indicating absence of current ideation. We will use random effects logistic regression with repeated measures to test for between-group differences in the occurrence of suicide ideation in the previous time period. The model will include one between-group variable (MBCT-S vs. TAU), one repeated measure (Times 1-5), and group by time interactions to assess for between-group differences during the five time periods. The model will specify intra-subject correlation as a random effect nested within site (which will be specified as a fixed effect). As described above, therapist will be treated as a partially nested fixed effect. Potential confounders will be entered as covariates and linear contrasts will test if MBCT-S produces greater reductions than TAU in the occurrence of suicide ideation at each time period.

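### Hypothesis 1.2.4 predicts lower Beck SSI scores, but the visible plan analyses the SSI only as present or absent and mislabels the period it covers

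*Combined protocol and SAP*

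**What the plan says.** Section 1.2, hypothesis 1.2.4, predicts that "MBCT-S subjects will have lower scores on the Beck Scale for Suicide Ideation", together with the Beck depression and hopelessness scales. The amendment log (entry of 10-21-13) records that 1.2.4 was edited to name these scales.

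Section 4.2 describes the SSI in two ways. The opening account of the outcomes says that it "provides a dichotomous (yes-no) measure of the presence or absence of ideation" and gives severity to the C-SSRS. The entry for the instrument itself presents the SSI as a further measure of ideation severity. It says that the scale is given at baseline and every follow-up and covers attitudes, "behaviors, and plans to commit suicide during the past week".

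Section 5, under H3a, adopts the first description. It says that the SSI "only allows calculations of suicide severity for those screening positive for ideation and so produces scores that tend to be highly skewed", and that for this reason "we are using the SSI to determine presence or absence of ideation". A zero on both screening items is read as "indicating absence of current ideation". This binary variable goes into a random-effects logistic regression over Times 1-5 with group-by-time terms, whose purpose is "to test for between-group differences in the occurrence of suicide ideation in the previous time period". Severity (0 to 5) and intensity (0 to 25) are then analysed by mixed models, both from the C-SSRS.

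**The concern.** A hypothesis about scores needs an analysis of scores. Here the hypothesis names SSI scores, while the analysis section explains why they will not be used and describes no model for them. The two quantities can part company: treatment could lower the intensity of ideation in veterans who continue to screen positive without changing how many screen positive. The yes/no model cannot see such an effect. Because Section 4.2 supports both uses of the SSI, it is also left open which one will count as the test of 1.2.4, and that choice could be made after the data are seen.

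The second matter is a label. A scale with a one-week look-back describes ideation around each visit. If the result is reported under the wording of Section 5, a reader may take it to describe the whole interval since the last visit.

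**Working it through.** The documents state no figure on this point, so there is none to reproduce. The check is a comparison of sections and two short calculations.

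**Step 1. Follow the SSI through the document.**

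| Place | Role of the SSI |
|---|---|
| Section 1.2, hypothesis 1.2.4 | Score, predicted to be lower with MBCT-S |
| Section 4.2, opening account of outcomes | Yes/no |
| Section 4.2, SSI entry | Ideation severity, past week |
| Section 5, H3a, first analysis | Yes/no, from two screening items |
| Section 5, severity and intensity models | Not used; C-SSRS only |

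Two entries call for a score and two for a binary variable. The only model that uses the SSI is binary.

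**Step 2. Can the binary model stand in for a test of scores?** Let p be the proportion screening positive and m the mean score among positives. With screen-negatives scored 0, the overall mean is p × m. The documents give neither p nor m, so these values are assumptions: p = 0.40 in both arms, m = 20 with TAU and 10 with MBCT-S.

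- TAU: 0.40 × 20 = 8.0
- MBCT-S: 0.40 × 10 = 4.0
- Yes/no comparison: 40% against 40%, odds ratio 1

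The hypothesis of lower scores is true in this example and the planned SSI model shows nothing. The result does not depend on 40%: for any common p above 0, the difference in means is 20p − 10p = 10p points while the odds ratio stays at 1. The reverse also limits the concern. If p falls and m is unchanged, the mean falls too, so a difference in presence is indirect evidence on scores, but it is not a test of them.

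**Step 3. The look-back against the interval.** The SSI covers 1 week (Section 4.2). Times 4 and 5 are at 6 and 12 months (Section 3), which are about 26 weeks apart. The share of that interval covered at Time 5 is 1/26 = 3.8%. I give no fixed share for the earlier intervals: Section 3 places Times 2 and 3 at weeks 4 and 8, but the amendment log moves Time 2 to week 6 and then ties both visits to treatment progress.

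**Step 4. What the phrase about the previous period can mean.** H1b in Section 5 counts events during each assessment period, which favours the interval between visits. Against that, the sentence before the phrase speaks of current ideation, and five assessments have only four intervals between them, with none before Time 1. The phrase is ambiguous; on the interval reading it does not match the instrument.

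**The case against.** The strongest reply is that the yes/no choice is deliberate and explained. SSI severity exists only for those who screen positive, the scores are skewed, and the C-SSRS lets every participant enter the severity analysis. That is a sound reason for the analysis, and it means that ideation severity under objective 1.1.3 is tested. It does not bring hypothesis 1.2.4 into line, since that hypothesis names the SSI and its scores.

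Second, Section 5 mentions remaining mixed models to be described below, and none follows, not even for depression or hopelessness. An SSI score model may have been intended there. This cannot be excluded, which is why the point is limited to the visible plan; the reasoning given under H3a argues against such a model.

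Third, Section 5 defines the binary variable correctly as current ideation, and the test is the same under either label. That stands, and it makes the second half of the point a correction of wording.

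A reader might go further and infer that the report would greatly undercount veterans with any ideation over each interval. The documents do not support this. They commit to a between-group test, not to reporting cumulative occurrence. They also give no weekly risk of ideation and nothing on how strongly weeks correlate within a person, so the size of any undercount cannot be derived.

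**Conclusion.** The SSI part of hypothesis 1.2.4 has no matching analysis in the visible plan, and Section 4.2 contradicts itself on whether the SSI is a severity measure or a yes/no measure. The consequence is confined to one secondary hypothesis: a lowering of scores among persistent screen-positives would go undetected on the SSI, although the C-SSRS severity and intensity models might pick it up. The example of 8.0 against 4.0 shows that the two analyses can disagree completely. It rests on assumed values and is not a forecast.

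The period label is a smaller fault. It overstates what a one-week measure observes, by most in the last interval, where about 4% is covered. It would be wrong to infer that the between-arm comparison is invalid: both arms use the same look-back, and the comparison of past-week ideation is sound once it is named as such. The primary analysis and the sample size are not affected.

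**What to change.** Settle the role of the SSI before the analysis, in one of two ways.

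- **Change the hypothesis.** Reword 1.2.4 to predict a lower proportion with past-week ideation on the SSI, and lower C-SSRS severity and intensity. This needs no new model or data. The cost is giving up a claim about SSI scores.
- **Add an analysis.** Prespecify a model of the SSI total in all participants, scoring 0 for those who answer 0 on both screening items, with a method suited to skewed data with many zeros, such as an ordinal or two-part model. With a two-part model, state the overall effect as well, because a comparison among screen-positives alone is not a randomised one. The SSI is already given at every assessment, so the cost is one more secondary test, to be counted under the Bonferroni provision in Section 5.

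Then make the two descriptions of the SSI in Section 4.2 agree with the choice.

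In Section 5, H3a, state the binary outcome as ideation in the week before each assessment and limit conclusions to past-week ideation. This is a change of wording only. Occurrence over the whole interval should not simply be moved to the C-SSRS, because the documents do not say what period its ideation items cover at follow-up.

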MBCT-S. The proposed intervention was adapted to work in unison with the VA's current suicide prevention practices by incorporating into the standard MBCT program exercises that build on the VA Safety Plan to address the risk of suicide. If our intervention is found to be efficacious, we believe that

the integration of the intervention with existing strategies for suicide prevention will enhance its potential for implementation.

Approximately 5-10 participants will be enrolled per group. The standard MBCT program consists of 8 weekly 2-hour sessions, with daily home practice, including regular meditation and mindful movement practice for about one hour per day for 6 days a week. The core skill addressed in the standard MBCT protocol is the ability to "recognize and disengage from mind states characterized by self-perpetuating patterns of ruminative, negative thoughts."₃ Each class begins with a brief discussion of the theme and class curriculum, followed by in-class practice, and ends with a discussion of the immediate effects of the practice. MBCT-S maintains the same class structure and basic exercises as MBCT. In adapting the program for suicide, MBCT-S focuses primarily on Safety Plan Steps 1 and 2, providing exercises aimed at promoting patient awareness and recognition of the warning thoughts, feelings and situations identified as triggers on the Safety Plan (Step 1) and identifying and using positive internal coping responses (the mindfulness "skillful response") to these warnings (Step 2). Each patient uses their own Safety Plan, with specific triggers they identified in conjunction with their suicide prevention case manager. The identification of triggers may be further enhanced during group and individual MBCT-S sessions. MBCT-S classes will be led by two clinical psychologists. Both clinicians have been collaborating as part of our team in developing and delivering mindfulness-based interventions.

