MBCT-S is designed to achieve a transitional model via its session structure, which involves two individual sessions in the inpatient setting and 6 group outpatient sessions. We expect MBCT-S to promote continuity between inpatient and outpatient treatment phases by establishing a therapeutic alliance prior to the inpatient-outpatient transition that will be relied upon to improve outpatient engagement. The first 2 individual inpatient sessions are geared to introducing the patient to the program and the basic concepts of mindfulness, reviewing each patient's personal Safety Plan, enhancing the identification of suicide triggers identified on the Safety Plan, introducing the application of mindful awareness of suicide triggers and providing personalized guidance on establishing a home practice. The remaining group outpatient sessions are devoted to enhancing the ability to apply mindfulness to the thoughts, feelings and situations likely to trigger suicidal thinking.

MBCT-S adopts a patient-centered model in a number of ways. Unlike purely group-based approaches, MBCT-S's initial use of individual sessions provides a phase where the treatment rationale and goals can be individualized. This will rely heavily on tying the treatment to the Suicide Safety Plan, which is itself highly individualized. Patient-centeredness is also achieved through a design that is compatible with the population's needs and preferences. The VA's own data show that veterans at risk of suicide demonstrate significant difficulty engaging with treatments that are long-term and of high intensity, with no VISNs meeting the annual high risk suicide performance monitor for required mental health visits as of October, 2011. Thus, MBCT-S, which is shorter term and partially completed prior to discharge, was in part selected to better match the treatment utilization patterns of this population. Moreover, the intervention was specifically designed to address the challenge of outpatient continuity among patients with a myriad of presenting problems. Achieving this type of continuity requires an engagement-oriented approach that emphasizes patient support.

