We will also employ methods to examine the possible effects of both therapist and site on study outcomes by testing for nesting effects in our models. For the therapist variable, we will use a partially nested design₁₁, since therapist effects will be analyzed for treatment group participants only. In the case of mixed-effects models, therapist and site variables will be entered as fixed effects since the limited number of therapists and sites in the proposed study (2 each)₁₂ constrains the generalizability of inferences that could be derived from specifying random effects. We have modified the description of our analyses below to specify how we will test for site and therapist effects in each case.

For H1a, survival time analyses to compare MBCT-S to TAU will be run once at 12 months post-baseline using the Cox proportional-hazards regression model to test for group differences in the time from baseline to first in-study suicide event. Site will be entered as a nesting factor into the regression. For the therapist variable, we will test for a partially nested effect, simplifying assumptions regarding the patterns of clustering related to the use of a primary therapist or primary group. The regression analysis will also allow us to control for censoring effects due to the differential length of follow-up or the completion of follow-up without a repeat suicide event. However, if the proportional hazard assumption is not met, we will utilize other approaches to survival analysis, such as the log-rank test.

For H1b, we will obtain a count of "suicide events" during each assessment period, including baseline. Given that suicide events occur infrequently and have a non-normal distribution, a mixed-effects Poisson regression will make a between-group comparison with events as the dependent variable, one between-group variable (MBCT-S vs. TAU), one repeated factor for the multiple assessments, and a group by time interaction. The model will specify intra-subject correlation as a random effect nested within site (which will be specified as a fixed effect) and we will test for a partially nested effect for therapist as specified above. We will consider several correlational structures between repeated measures (e.g., compound symmetry) and determine the best structure using the Akaike's Information Criterion (AIC). Potential confounders that meet the p<0.10 criterion stated above will be entered as covariates.

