For severity of ideation, we will use mixed models analysis to make between-group comparisons with "severity of ideation" as the dependent variable, one between-group variable (MBCT-S vs. TAU), one repeated measure (Times 1-5), and group by time interactions. We will consider several correlational structures between repeated measures (e.g., compound symmetry) and determine the best structure using the Akaike's Information Criterion (AIC). Potential confounders that meet the p<0.10 criterion stated above will be entered as covariates. Linear contrasts will test between-group differences in "severity of ideation" separately at each time point. The same mixed models analytic strategy will be used to assess "intensity of ideation," with "intensity" as the dependent variable, MBCT-S vs. TAU as the between-group variable, the five time periods as the repeated measure and group by time interactions. As in the analysis for severity, we will determine the best correlational structure between-group differences in "intensity" at each time point. For both severity and intensity, as well as for all remaining mixed models analyses described below, we will control for site as a nested fixed effect and therapist as a partially nested fixed effect.

6. Data and Safety Monitoring

In addition to the detailed measures described above to maintain the safety of research participants and their data, this study will have a Data and Safety Monitoring Board (DSMB), which will serve as an oversight committee, reviewing any modifications to the research design and conduct of the study and making recommendations according to the NIH Policies for data and safety monitoring as described below. Definition of Adverse Events and Serious Adverse Events will be determined in accordance with the DSMB and the IRB. Reports of adverse events will be made to the IRB according to the standards for expedited reporting.

The individuals who will serve on the DSMB are:

The specific goals of this joint DSMB are:

- 1. To review new or modifications to risk management protocols at both sites.
- 2. To review procedures and decisions regarding the adequate protection of specific patients when
- investigators move into risk management protocols because of adverse events or clinical deterioration.
- 3. Review progress toward meeting enrollment goals.
- 4. To review procedures for maintaining the confidentiality of data, and quality of data collection, management, and analyses.

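### The ideation severity and intensity mixed models have no therapy-group term, although MBCT-S is given largely in groups; if outcomes correlate within groups, these secondary contrasts have standard errors that are too small

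*Combined protocol and SAP*

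**What the plan says.** **Delivery.** Section 4.1 describes a session structure "which involves two individual sessions in the inpatient setting and 6 group outpatient sessions", and states: "Approximately 5-10 participants will be enrolled per group". Item 1 of the Protocol Amendments refers to 8 weeks of group sessions, and item 3 to a group start date. On either session count, most of the treatment is given in groups that run as dated cohorts.

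**Severity and intensity models (section 5).** The terms listed are arm, time, arm by time, confounders that pass the screening criterion, a repeated-measures correlation structure chosen by AIC, and then: "we will control for site as a nested fixed effect and therapist as a partially nested fixed effect". Severity is compared between arms "separately at each time point", and intensity is handled the same way. The closing sentence extends the site and therapist terms to these two outcomes "as well as for all remaining mixed models analyses described below". No further model is written out after it, so depression and hopelessness are reached only through that sentence.

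**H3a logistic model (section 5).** It has a subject random effect and fixed site, and adds: "As described above, therapist will be treated as a partially nested fixed effect". Its contrasts are described as follows: "linear contrasts will test if MBCT-S produces greater reductions than TAU in the occurrence of suicide ideation at each time period".

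**Where the therapy group is mentioned.** In section 5 it appears once, in the H1a Cox paragraph, in a phrase about "simplifying assumptions regarding the patterns of clustering related to the use of a primary therapist or primary group". No method is attached. The H1b Poisson paragraph refers back to that treatment of therapist.

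**The concern.** Patients who share a therapy group share sessions, discussion, leader and calendar period, so their later scores may be alike. The terms in the severity and intensity models do not absorb this:

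- The repeated-measures structure handles correlation within a patient, not between patients.
- A two-level therapist effect removes only the average difference between therapists, not variation among 8-17 groups. If the two psychologists lead classes together, which section 4.1 leaves open, it removes none of it.
- The plan justifies fixed effects by the small number of therapists and sites (2 each). That reason does not carry over to 8-17 groups.

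If the correlation is positive, the MBCT-S mean at a post-treatment visit is less precise than the model reports. P-values are then too small and intervals too narrow. These outcomes bear on objective 1.1.3 and are tested at p < 0.05, although section 4.2 treats them as exploratory beside the event and attempt outcomes.

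**Working it through.** **Inputs from the documents.** 82 per arm, 66 per arm after 20% attrition (section 3.3); about 5-10 per therapy group (section 4.1); two therapists and two sites as fixed effects (section 5). The plan gives no sample size or power for these models, so there is no plan figure to reproduce. The 164 in section 3.3 is for time to first event and is used here only for arm size.

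**Assumed, because the documents are silent.** ICC 0.01-0.10; proportion p of MBCT-S patients who attend a group 0.7-1.0; TAU patients independent.

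**Number of groups.** 82/10 = 8.2 and 82/5 = 16.4, so about 8-17.

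**Formula.** Scale the outcome variance to 1. Of m patients assigned to a group, mp attend and share the correlation. The variance of the MBCT-S mean is (1/n)[1 + p(mp - 1)ICC]; for TAU it is 1/n. The true variance of a single-time contrast, relative to the variance the model reports, is

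f = [2 + p(mp - 1)ICC]/2, and actual type I error = 2[1 - Phi(1.96/sqrt(f))].

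**Worked case, m = 8, ICC 0.05.**
- p = 1: f = (2 + 7 x 0.05)/2 = 1.175, type I error 7.1%.
- p = 0.8: f = (2 + 0.8 x 5.4 x 0.05)/2 = 1.108, 6.3%.
- p = 0.7: f = (2 + 0.7 x 4.6 x 0.05)/2 = 1.081, 5.9%.

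**Range of type I error.**

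| m | ICC | p = 1 | p = 0.8 | p = 0.7 |
|---|---|---|---|---|
| 5 | 0.01 | 5.2% | 5.1% | 5.1% |
| 10 | 0.01 | 5.5% | 5.3% | 5.2% |
| 5 | 0.05 | 6.2% | 5.7% | 5.5% |
| 8 | 0.05 | 7.1% | 6.3% | 5.9% |
| 10 | 0.05 | 7.7% | 6.6% | 6.2% |
| 5 | 0.10 | 7.4% | 6.4% | 6.0% |
| 10 | 0.10 | 10.4% | 8.3% | 7.5% |

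If 5-10 counts actual attenders, f = [2 + p(m - 1)ICC]/2. At p = 0.8 and 0.7 this gives 6.6% and 6.4% for (8, 0.05), and 9.3% and 8.7% for (10, 0.10).

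**Attrition.** With 80% still observed, observed groups shrink to 0.8m and f = [2 + p(0.8mp - 1)ICC]/2. At p = 0.8, (8, 0.05) gives f = 1.082 and 6.0%; (10, 0.10) gives f = 1.216 and 7.6%. This applies near 12 months; earlier visits change less.

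**Does the planned therapist effect help?** In a single-time simulation (20,000 runs, 82 per arm, all attending, therapist fixed in the MBCT-S arm, no group term), type I error was 5.1% at ICC 0, 7.1% at (8, 0.05) and 10.3% at (10, 0.10). It does not remove the inflation.

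**H3a logistic model, single-time contrast.** This was simulated with 5,000 runs, an assumed ideation prevalence of 70/50/40/40/40% over the five times, random-intercept variance 2.25 and a latent-scale ICC. Monte Carlo error is about 0.3-0.4 points. At ICC 0 the type I error was 5.1%-5.5%. At p = 1, 0.8 and 0.7 it was 6.7%, 5.5% and 5.9% for (8, 0.05), and 8.8%, 7.5% and 6.2% for (10, 0.10).

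**The case against.** **The plan already addresses clustering.** It adopts a partially nested design and the Cox paragraph mentions the group. The H3a logistic paragraph points back with "As described above, therapist will be treated as a partially nested fixed effect", which may or may not bring the group wording with it, so the gap there is less clear-cut. For severity and intensity there is no such pointer, and the terms listed are site and therapist only. That part stands.

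**The size is conditional and often small.** This is correct. Without a stated ICC, inflation cannot be shown to occur. At ICC 0.01 it is negligible; in the middle case with 70%-80% attending it is 5.9%-6.3%, and less near 12 months. Figures of 8%-10% need larger groups, a high ICC and high attendance together. For the logistic model at ICC 0.05 with partial attendance, the result is barely distinguishable from no clustering.

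**TAU may not be independent.** Item 3 of the Protocol Amendments matches controls to treated patients in blocks by consent date and group start date. Any calendar component would then be shared by both arms and partly cancel in the contrast. That would reduce the figures, but it does not remove what arises within the therapy group itself.

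**Stronger readings to avoid.** A reader might infer that the plan ignores therapy groups throughout, or that the primary result is unsafe. The documents do not support either: the H1a paragraph names the group as a source of clustering, H1b refers back to it, and what is missing there is a method. Nor can one say that the depression and hopelessness models omit the term, because they are not written out.

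**Conclusion.** The concern holds for the C-SSRS severity and intensity models. Nothing in the documents adds a therapy-group term to them, and the existing terms cannot stand in for one. Under positive within-group correlation, single-time post-treatment contrasts are anti-conservative: about 5.1%-10.4% actual type I error over ICC 0.01-0.10, groups of 5-10 and 70%-100% attending. These figures rest on assumed ICC and attendance and on independent TAU patients; the full-attendance column is close to an upper bound for each ICC. Any depression or hopelessness model run under the same general sentence would share the problem. This is a worthwhile correction to secondary analyses. It does not show an error in the primary Cox analysis; the Cox and Poisson models need clarification only.

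**What to change.** **Severity and intensity models, and any depression or hopelessness models run under the same sentence.** Add a therapy-group random effect in the MBCT-S arm only, acting at post-baseline times, with Satterthwaite or Kenward-Roger degrees of freedom. Treat TAU patients, and MBCT-S patients who never join a group, as singletons, and fix that rule in advance. A cluster-robust variance with a small-sample correction is an acceptable alternative. In simulation the random effect with Satterthwaite-type degrees of freedom brought type I error back to about 4%-5%, and the corrected robust variance gave 4.6%-5.5%. Fixed site and therapist effects may stay.

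**H3a logistic model.** Do the same, and say so explicitly. The corrected robust variance gave 4.2%-5.1% there.

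**Cox and H1b models.** State only how the existing reference to the primary group is to be applied.

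**Cost.** SAP wording, one variance component, and a record of who joined which group. If the ICC is zero, degrees of freedom fall to about 4/[1/(G - 1) + 1/81] for G groups. G = 17 gives 53 (t = 2.005) and G = 9 gives 29 (t = 2.045), against t = 1.975, so single-time intervals widen by about 1.5% to 3.5%. If the ICC is above zero they widen more, but that is the correct uncertainty, not a penalty.
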